## HUMAN SUBJECTS

### 1. Risks to Human Subjects

#### a) Human Subjects Involvement, Characteristics, and Design

This is a prospective single center double-blind placebo-controlled randomized clinical trial in human subjects with chronic heart failure. Since iron metabolism varies greatly among different mammalian species, it is necessary to study human subjects in order to obtain relevant information that might eventually favorably impact human health.

The study entry criteria are as follows:

Inclusion Criteria:

- Age 21-75 years
- Symptomatic NYHA Class II-III heart failure >3 months
- Guideline-recommended heart failure treatment for > 3 months
- Hemoglobin >10 g/dl for men and >9 g/dl for women
- Functional iron deficiency (defined as serum ferritin level <100 ng/ml or between 100 and 299 ng/ml with transferrin saturation <20%)
- Left ventricular ejection fraction <40%, or left ventricular ejection fraction ≥40% with left atrial enlargement (left atrial volume index >28 ml/m^2) and/or left ventricular hypertrophy (left ventricular mass index >95 g/m^2 (women) or >115 g/m^2 (men) determined by echocardiogram within last 24 months.
- Able and willing to provide written informed consent

Exclusion Criteria:

- Presence of implantable defibrillator, permanent pacemaker, other metal implant not compatible with 3TMR/MRI, or other contraindication to 3T MRS/MRI procedures
- Heart failure due to infiltrative cardiomyopathy, restrictive cardiomyopathy, or hypertrophic cardiomyopathy
- Weight <50 kg or >120 kg
- Height < 5 feet 4 inches (1.63 m)
- Coronary or cerebral atherothrombotic events in the past 6 months
- Hospitalization of emergency room visit for heart failure within past 3 months
- ICD shock in last 3 months
- Known peripheral artery disease or ankle-brachial index <0.9 at screening visit
- Exercise primarily limited by angina, lung disease or neuromuscular disease
- Systolic blood pressure <100 or >160 mmHg
- Heart rate <50 or >110 min
- Estimated glomerular filtration rate <30 ml/min
- Liver function tests >3 times upper limit of normal
- Serum phosphate below normal limit
- Pregnant or breast-feeding women
- Women of child-bearing potential unwilling to use recommended contraception methods during the study
- Treatment with intravenous iron in past year
- Treatment with erythropoiesis stimulating agents in the past year
- Known intolerance of intravenous iron
- History of anaphylaxis
- Participation in another clinical trial within last 30 days.

Recruitment strategy. We will use admission and emergency department logs, clinic appointment logs, and other existing electronic hospital information systems to identify potentially eligible subjects from within our clinical practice. Clinical personnel in the NYU Heart Failure program meet on a weekly basis to identify potential study subjects. An experienced research coordinator will initiate contact with the attending physician

to obtain additional information on potential eligibility and permission to approach the subject. Based on historical data from the NYU Heart Failure Quality Improvement Program case identifications over the past year, there are approximately 1200 annual discharges with primary HF diagnosis from NYU Langone Medical Center (Tisch, Bellevue, and Manhattan VA hospitals). If we conservatively estimate that 50% of those admissions are re-admissions, then approximately 1800 unique heart failure cases will be identified over the proposed 18-month period of enrollment (100 unique cases/month). For the pilot study presented above, this recruitment strategy allowed us to enroll eight subjects over 3 months. Accordingly, we believe that this clinical volume is sufficient to support our proposed enrollment target of 1-2 randomized subjects per month.

We will also recruit patients at NYU Langone Health with use of the MyChart patient portal of the EPIC electronic health record. A DATACORE query of the EPIC database will be conducted to identify potentially eligible subjects (based on inclusion criteria of age 21-75 years, ICD9 and ICD10 codes for acute, chronic, and acute on chronic systolic heart failure, and acute, chronic, and acute on chronic diastolic heart failure, and exclusion criteria of ICD codes for permanent pacemaker or implantable defibrillators). After approval from DATACORE, an invitation letter will be placed in MyChart (text of invitation letter is attached in Research Navigator).

We will also recruit patients using printed advertisements in the free morning newspaper, AM New York, and electronic advertisement on Facebook pages with content relevant to heart failure patient. The advertisement text is attached in Research Navigator.

A telephone script for respondents to MyChart invitation letters, and print and electronic advertisements is attached in Research Navigator. Personal identifiers will only be recorded for respondents who meet eligibility for a screening visit and express willingness to be scheduled for a screening visit.

There are no vulnerable populations enrolled in this study.

There are no collaborating sites for this study. All research data will be created and analyzed at NYULMC.

## **b) Sources of Materials**

The research material generated in this protocol will consist of clinical assessments, laboratory measurements and physiological measurements obtained from the human subject participants.

Historical information related to demographics and the cause, severity, and treatment of heart failure will be recorded from the medical record or obtained by subject interview. Other research data will be obtained as a result of completion of the research procedures described above. These data include blood test results, 6-minute walking test results, and the results of the 31P-MRS and MRI analysis of skeletal muscle bioenergetics in response to plantar flexion exercise. There will be no data collection related to prospective clinical testing or clinical care. The research database will not retain any identifiers after completion of study procedures.

The Principal Investigator and other trained study personnel will have access to private health information only during active participation in the study. This information will be used only for scheduling participant visits, for confirmation of correct identity at study visits, and for review of medical records as described in study procedures. All identifying information will be kept separate from the other research records in a locked cabinet in a locked room or on a secure electronic database. All identifiers (except signed consent forms) will be destroyed after the subject has completed the last visit. No identifiers will be retained in the research database after completion of study procedures.

A random Study ID code will be assigned to each participant. This code will be used on all written and electronic research records. The Principal Investigator and study coordinator will be able to link the Study ID code back to the personal information during the interval of active participation in the study, but this link will be destroyed after the subject has completed the study procedures. Primary source documents with identifiers including signed consent forms and contact information will be kept separately in a locked cabinet in a locked room. All primary source documents with identifiers (except signed consent forms) will be destroyed after the subject has completed the last visit. Other primary source documents including case report forms, laboratory reports, and results of the 6-minute walking test, and the 31P-MRS and MRI analysis of skeletal muscle bioenergetics in response to plantar flexion exercise will be kept in a project notebook in a locked cabinet in a locked office. Research data without identifiers will be recorded on the NYULMC REDCap system. The REDCap system provides secure password protected storage of research information behind the NYU firewall and provides quality control and audit trail functions to validate the integrity and quality of the research data.

### c. Potential Risks

The risks of the research procedures in this protocol are generally similar to the risks of the same procedures performed in the course of clinical care. The potential risks to study participants are as follows;

**Risk of ferric carboxymaltose (Injectafer®):** Ferric Carboxymaltose (Injectafer®, 750 mg iron/15 ml single use vial) has been demonstrated to be safe and effective in the treatment of iron deficiency anemia and is FDA-approved for treatment of iron deficiency in adult patients. The most common adverse reactions recorded in clinical trials (>2%) are nausea, hypertension, flushing, hypophosphatemia, and dizziness. Rare occurrences of anaphylactic or anaphylactoid reactions have also been reported. The dosing and route of administration used in this study are consistent with the FDA-approved prescribing information for this drug. In the FAIR-HF study, ferric carboxymaltose was administered repeatedly over 6 months to 304 subjects with chronic heart failure. Reported adverse events did not differ from placebo. There were no anaphylaxis events or other allergic reaction events reported. In the CONFIRM-HF study, 150 heart failure subjects received intravenous ferric carboxymaltose for 1 year. Overall adverse events did not differ from placebo. There were no anaphylaxis events, but there was one episode of rash, one episode of urticaria, and one episode of flushing reported in the ferric carboxymaltose group. Taken together, this reported experience of repeated dosing of ferric carboxymaltose over 6-12 months in a combined group of 454 patients with heart failure does not suggest a signal of increased risk of adverse effects in heart failure when compared to clinical trial population data included in the package label.

#### Risks of MRI:

**Magnetic Field Risks:** MRI uses a strong magnetic field to create images of the body. Because of the strong magnetic field, the metal objects within the body or within the MRI room could cause injury. Subjects with metal implants will be excluded from the study. Standard operating procedures in MRI rooms check for any possible external metal objects before the scan.

**Risk of Anxiety/Claustrophobia:** The MRI scans are obtained in a small space that may be stressful for some subjects with claustrophobia. We will exclude subjects with known claustrophobia and terminate the MRI scan upon subject request.

**Risk of High Noise Levels:** The MRI scanner produces loud noises that may increase anxiety in some subjects. Disposable earplugs to reduce the noise levels but will still allow voice communication with the scanner operator will be provided to all subjects.

**Risk of MRI Systems Failure (Quench):** This is a rare event caused by loss of the magnetic field. Subjects will be immediately brought out of the magnet room if system failure is detected.

**Risk of Neurostimulation:** Some subjects may experience muscle twitches or tingling sensations and a slight increase in body temperature during some types of scan activity. These are very unlikely under current MRI guidelines.

**Risks in Pregnant Women:** Although there are no known risks of MRI on pregnant women or a fetus, there is a possibility of yet undiscovered pregnancy related risks. Since there is no direct benefit from participating in this protocol for a pregnant woman, we will exclude pregnant women. If a woman becomes pregnant during the study, we will request to follow the health of the mother and fetus during pregnancy, and the health of the mother and child for 30 days after delivery.

**Incidental MRI findings:** The MRI scan is for research purposes only and is not directed toward or designed for clinical diagnosis. Per Department of Radiology procedures, all MRI scans will be reviewed by a clinical radiologist, and any abnormal findings will be reported to the subject, and the subject's physician.

**Risk of phlebotomy:** Phlebotomy is commonly associated with transient pain and minor bleeding at the needle site, and rarely major bleeding, infection or vasovagal reaction with transient hypotension. The risks of phlebotomy in this study do not differ from risks of phlebotomy for clinical blood tests.

**Risk of intravenous line:** Placement of an intravenous catheter is commonly associated with transient pain and minor bleeding at the needle site, and rarely major bleeding, infection or vasovagal reaction with transient hypotension. The risks of placement of an intravenous catheter in this study do not differ from risks of phlebotomy.

### Other Study Risks:

**Risk of exercise:** The 6-minute walk test is a self-limited submaximal exercise test in which the study subject selects the walking pace and has the option to stop and rest as needed. Since the purpose of this test is to simulate daily walking activity, the small risks associated with submaximal exercise do not substantially differ from risk associated with exercise in daily activities. A study with over 2000 elderly subjects demonstrated no serious adverse events associated with the 6-minute walk test. The plantar flexion exercise during the 31P-MRS and MRI procedure consists of rhythmic plantar flexion against low resistance and is akin to stepping on a brake or gas pedal in a car. Accordingly, the small risk associated with this submaximal exercise does not substantially differ from risk associated with exercise in daily activities.

**Risk of breach of confidentiality:** There is a small risk of breach of confidentiality of protected health information related to participation in this protocol.

## 2. Adequacy of Protection Against Risks

### a. Recruitment and Informed Consent

Recruitment will be conducted in accordance of the policies of the New York University IRB and FDA regulation 21CFR, Part 50. Potential subjects will be identified by the primary cardiologist supervising patient care during periods of clinical stability in an ambulatory care setting. The primary cardiologist will determine whether the potential participant is willing to consider discussion of the study with research staff. If the primary cardiologist determines that the potential participant is willing to discuss the study, research staff will provide the potential participant with additional information about the study and offer the opportunity to read the IRB-approved consent form. The rationale, procedures and potential risks of the procedures in the study will be explained to each participant by the Principal Investigator or his appointed designee. Each subject will be told that participation in the studies described in this proposal is strictly voluntary, that refusal to participate will not alter the patient's relationship with her physician, that the studies constitute research and that the information obtained may increase understanding of the role of body iron and exercise in general but will not be specifically helpful to the individual patient's care. The subject's comprehension of the major aspects of the study procedures, study risks, and study benefits will be determined by asking the subject to respond to questions about the study. A signed, IRB-approved informed consent form will be obtained from each subject by the Principal Investigator or his designee on the day of the enrollment. A copy of the most current version of the IRB-approved Patient Informed Consent Form, along with a copy of each subject's signed and dated consent form will be kept in a designated research administrative file in a locked cabinet in a locked room. A signed copy of the consent form will be given to each subject. Due to the complexity of the study procedures, only subjects able to speak either English or Spanish will be enrolled. For Spanish speaking subjects, the entire consent process will be conducted in Spanish by a fluent native Spanish-speaking member of the research staff. A Spanish consent form will be created and submitted to the IRB after final IRB-approval of the English language consent form.

### b. Protections Against Risk

The study is deemed to be greater than minimal risk, primarily due to the potential side effects of ferric carboxymaltose. To minimize risk, all procedures will be performed in clinically stable subjects who meet eligibility criteria under the direct supervision of the principal investigator, and/or other trained study personnel. All study procedures are performed within the CTSI Clinical Research Center or MRI Center with nearby access to emergency procedures in the event of unanticipated deterioration in clinical status.

Participant risks are also minimized by the following protections described in the study protocol:

- Study entry criteria to exclude potential participants at greater risk of adverse events
- Administration of the study agent, ferric carboxymaltose, according to the FDA-approved prescribing information
- Active surveillance for potential study drug adverse effects and other adverse events
- Pre-specified criteria for participant withdrawal to protect participant safety
- Pre-specified criteria for study termination or suspension to protect participant safety
- Use of the MRI imaging center standard clinical protocol to prevent transport of ferromagnetic materials into the imaging environment
- Safety monitoring by the Principal Investigator

No vulnerable subject populations will be enrolled in this study.

All research subject data will be kept strictly confidential, except when published for purposes of reporting data. In that case, the subjects are never identified. All electronic data will be de-identified and transmitted and stored with secure systems that meet or exceed Federal guidelines (REDCap database behind NYU firewall). The Principal Investigator will maintain files with identifying information in a locked cabinet in a locked room.

### **c. Potential Benefits of the Proposed Research to Human Subjects and Others**

There is no expected benefit for participant in this study. The feasibility data acquired in this study may eventually help future heart failure patients, or patients with other diseases associated with functional iron deficiency.

### **d. Importance of the Knowledge to be Gained**

Anemia of chronic disease associated with inflammation and functional iron deficiency is the second most common cause of anemia worldwide. Functional iron deficiency is common in patients with heart failure and may be associated with impaired functional capacity and increased risk for hospitalization and death. Intravenous iron therapy has been shown to improve various measures of functional capacity, but the mechanism of action and target population with greatest likelihood has not been identified. This study is designed to provide proof-of-concept data to support future investigations of the role of iron in the pathogenesis of exercise intolerance. This line of investigation may eventually have impact on therapeutic strategies for maintenance of iron homeostasis in healthy populations, and heart failure and other chronic inflammatory disease populations.

### **e. Data and Safety Monitoring Plan**

The research procedures described in this protocol are deemed to be greater than minimal risk.

The Principal Investigator will serve as the medical monitor for the study and will be responsible for monitoring and reporting of adverse events to the NYU IRB according to the following definitions and procedures:

#### *Adverse Event Definitions*

An Adverse Event (AE) is any untoward medical occurrence in a clinical investigation subject administered a pharmaceutical product and does not necessarily require a causal relationship with the study treatment. An AE can therefore be any unfavorable and unintended sign (e.g., an abnormal laboratory finding), symptom, or disease temporarily associated with the use of a medicinal product, whether or not related to the study procedures. Diseases, signs, symptoms, or laboratory abnormalities already existing at the time of enrollment are not considered AEs unless they worsen (i.e., increase in intensity or frequency). Surgical procedures themselves are not adverse events; they are therapeutic measures for conditions that require surgery. The condition for which the surgery is required may be an AE. Surgical procedures planned prior to randomization and the conditions leading to these measures are not AEs unless the event exacerbates or worsens after randomization.

A Serious Adverse Event (SAE) is any untoward event that:

1. Is fatal
2. Is life-threatening
3. Results in persistent or significant disability or incapacity
4. Is a congenital abnormality or birth defect
5. Requires inpatient hospitalization or prolongation of existing hospitalization with the following exceptions:
  - Preplanned (prior to the study) hospital admissions unless the hospitalization is prolonged.
  - Planned admissions (as part of a study—e.g., routine biopsies)
  - 23 hour hospitalization or re-hospitalizations
  - Hospitalization for elective procedure (e.g. generator change for ICD or pacemaker)
  - Emergency department visits

Important medical events that may not result in death, be life-threatening, or require inpatient hospitalization may be considered an SAE when, based on appropriate medical judgment, they may jeopardize the patient and may require medical or surgical intervention to prevent one of the outcomes listed above.

**Life-threatening** indicates that the patient was, in the view of the investigator, at immediate risk of death from the adverse event as it occurred. It does not include an adverse event that, had it occurred in a more severe form, might have caused death.

**Persistent or significant disability/incapacity** indicates that the event resulted in permanent or significant and substantial disruption of the patients' ability to carry out normal life functions.

#### **Classification of Adverse Events**

The Principal Investigator will assess all AEs to determine the severity of the event, the possible causal relationship with study drug or study procedures, and whether the event is anticipated or unanticipated according to the following definitions:

1) **Severity.** The severity (intensity) of each AE will be determined by the Principle Investigator according to the following definitions:

**Mild:** Symptom(s) or sign(s) barely noticeable to the subject or does not make the subject uncomfortable. The AE does not influence performance or functioning. Treatments are not ordinarily needed for relief of symptom(s).

**Moderate:** Symptom(s) or sign(s) that cause the subject to be uncomfortable or may require downtitration of study drug. Treatment of symptom(s) may be needed.

**Severe:** Symptom(s) or sign(s) that cause the subject severe discomfort or may cause cessation of treatment with study drug. Treatment for symptom(s) are often needed.

**Life-threatening:** Symptom(s) or sign(s) of a sufficient severity/intensity to cause the subject to be at immediate risk of death. These cases will be classified as a Serious Adverse Event.

2) **Relationship to study procedures.** The temporal/causal relationship between the study procedures and the AE will be determined by the Principle Investigator according to the following definitions:

**Definite:** Clearly related to the study procedures.

**Probable:** Likely (high suspicion) related to the study procedures.

**Possible:** Possibly but not likely (low suspicion) related to the study procedures.

**Unrelated:** Clearly not related to the study procedures.

3) **Anticipated or unanticipated.** The relationship of the AE to the known side effect profile of the study drug and the known clinical manifestations of heart failure and other pre-existing co-morbid conditions will be determined by the Principal Investigator according to the following definitions:

**Anticipated:** Consistent with the known side effect profile of study drug or other study procedures and/or known clinical manifestations of heart failure or other pre-existing co-morbid conditions.

**Unanticipated:** Not known to be associated with study drug, other study procedures, heart failure, or other pre-existing co-morbid conditions.

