## STUDY DESIGN

The proposed study design is a prospective, single-center, randomized, double-blind, parallel group placebo-controlled study (Figure 2). Primary and secondary endpoints will be assessed before and 4 weeks after administration of ferric carboxymaltose or placebo. It is anticipated that the study will require 2 years to complete enrollment.

**Study population:** Up to 50 subjects will be recruited from the clinical practice of the NYU Advanced Cardiac Therapeutics group at NYU Langone Medical Center. 36 eligible subjects will be randomized. Study entry criteria are listed in the Human Subjects section below.

**Study visits:** The study will require 3 visits over approximately 8-10 weeks for each subject: Visit 1: Screening; Visit 2: Baseline primary and secondary endpoint measurements, randomization, and study drug administration; Visit 3: final assessment of primary and secondary endpoint measurements. Additional details of the procedures at each study visit are described below.

**Study agent and control description:** Ferric Carboxymaltose (Injectafer®, 750 mg iron/15 ml sterile single use vial) will be provided by the American Regent pharmaceuticals (Shirley, NY) to the NYU Investigational Pharmacy and stored in the NYU Investigational pharmacy at 20°C to 25°C according to manufacturer instructions. An IND exemption will be requested from the FDA. Ferric carboxymaltose is nonionic polynuclear iron (III) hydroxide carbohydrate complex that binds iron tightly and requires macrophage processing for release of iron into body stores. Ferric carboxymaltose has been demonstrated to be safe and effective in the treatment of iron deficiency anemia and is FDA-approved for treatment of iron deficiency in adult patients. The most common adverse reactions recorded in clinical trials (>2%) are nausea, hypertension, flushing, hypophosphatemia, and dizziness. The dosing and route of administration used in this study protocol are consistent with the FDA-approved prescribing information for this drug (see appendix for FDA-approved package insert) and prior studies of this agent in heart failure populations.

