**Medical History:** The following information will be obtained from review of the medical record and/or patient interview at Visit 1: 1) Left ventricular ejection fraction (date and imaging mode); 2) Etiology of heart failure (ischemic or non-ischemic); 3) Duration of heart failure (years); 4) NYHA Class (I-IV); 5) Co-morbid diseases (hypertension, hyperlipidemia, coronary artery disease, chronic kidney disease, chronic lung disease, atrial fibrillation); 6) Medications by pharmacological class: angiotensin converting enzyme inhibitors, angiotensin receptor blockers, beta-adrenergic receptor blockers, digitalis glycosides, loop diuretics, mineralocorticoid receptor antagonists, statins, aspirin, thienopyridines, warfarin, and novel oral anticoagulant agents; 7) Demographic information including age, sex, ethnicity; 8) Contact information including home, work and mobile phones, street address, email address (to be purged after completion of study visits).

**Heart Failure Symptoms:** The following information will be obtained from review of medical record and/or patient interview: 1) Functional capacity; 2) Orthopnea, paroxysmal nocturnal dyspnea, edema; 3) Medical resource use (doctor visit, emergency department visit, hospitalization); 4) Medication change; and 5) Use of appropriate measures to protect against pregnancy in women of childbearing potential.

**Cardiovascular examination:** Limited physical examination to assess evidence of congestion including assessment of jugular venous pressure, lung exam, cardiac exam, abdominal exam for hepatomegaly, and extremity exam for edema and perfusion.

**Safety Blood Monitoring:** Venous blood will be collected from a forearm vein with standard sterile venipuncture technique for analysis of biomarkers of iron stores (serum iron, total iron binding capacity, serum ferritin), complete blood count, comprehensive metabolic panel, serum phosphate, and beta-HCG (for women of childbearing potential) according to the schedule of assessments (Table 1). All laboratory analyses will be performed by the New York State licensed CLIA-compliant NYU Langone Medical Center Tisch Hospital Clinical Laboratory.

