#### **IRB Reporting**

Federal regulations require timely reporting by investigators to their local IRB of unanticipated problems posing risks to subjects or others. The following describes the NYULMC IRB reporting requirements, though Investigators at participating sites are responsible for meeting the specific requirements of their IRB of record.

Report Promptly, but no later than 5 working days:

Researchers are required to submit reports of the following problems promptly but no later than 5 working days from the time the investigator becomes aware of the event:

- *Unanticipated problems including adverse events* that are unexpected and related

- Unexpected: An event is “unexpected” when its specificity and severity are not accurately reflected in the protocol-related documents, such as the IRB-approved research protocol, any applicable investigator brochure, and the current IRB-approved informed consent document and other relevant sources of information, such as product labeling and package inserts.
- Related to the research procedures: An event is related to the research procedures if in the opinion of the principal investigator, the event was more likely than not to be caused by the research procedures.
- Harmful: either caused harm to subjects or others, or placed them at increased risk

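### The severity scale has no objective criteria for laboratory or vital-sign findings, so a symptom-free laboratory abnormality found after the single infusion is graded Mild whatever its size, short of impaired functioning or immediate risk of death

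*Combined protocol and SAP*

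**What the plan says.** Under Adverse Event Definitions, an adverse event can be "any unfavorable and unintended sign (e.g., an abnormal laboratory finding), symptom, or disease". Laboratory abnormalities are therefore adverse events, and Classification of Adverse Events, item 1, has the Principal Investigator give each adverse event one of four severity grades:

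- **Mild:** "Symptom(s) or sign(s) barely noticeable to the subject or does not make the subject uncomfortable". A further condition is "The AE does not influence performance or functioning".
- **Moderate:** "Symptom(s) or sign(s) that cause the subject to be uncomfortable or may require downtitration of study drug".
- **Severe:** "Symptom(s) or sign(s) that cause the subject severe discomfort or may cause cessation of treatment with study drug".
- **Life-threatening:** symptoms or signs that put the patient at immediate risk of death; these are also serious adverse events.

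The scale gives no laboratory or vital-sign thresholds, and the protocol cites no external toxicity scale.

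On the drug's known harms, Study Design states: "The most common adverse reactions recorded in clinical trials (>2%) are nausea, hypertension, flushing, hypophosphatemia, and dizziness". The Safety Blood Monitoring paragraph under Study Assessments lists "complete blood count, comprehensive metabolic panel, serum phosphate" among the tests. The Study Summary specifies a single dose, and Study drug administration gives it over 15 minutes. Under IRB Reporting, an event is unexpected when "its specificity and severity are not accurately reflected in the protocol-related documents".

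**The concern.** Severity is the field in the adverse event record that should convey how large a harm was. For a laboratory finding, size lies in the measured value, and patients often cannot feel it. This scale separates its first three grades by what the patient feels or by what might be done with study drug. If neither applies to a late blood result, a trivial and a profound abnormality receive the same label.

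This matters here because hypophosphatemia is one of five reactions the protocol names as common, and phosphate is measured after dosing. Phosphate below normal is also an exclusion criterion, so a low value at Visit 3 would normally be a new finding and hence an adverse event to be graded. The analysis plan names hemoglobin, ferritin and transferrin saturation as laboratory outcomes but not phosphate or liver tests. No planned comparison of values would make up for an uninformative grade on those two.

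**Working it through.** No arithmetic applies, and the plan states no figure to reproduce. The check is to apply each grade to one case: a laboratory abnormality on the Visit 3 safety bloods in a patient who feels nothing and functions as before.

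**Step 1. Does the scale apply?** Yes. Adverse Event Definitions treats an abnormal laboratory finding as a sign, and item 1 covers every adverse event.

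**Step 2. When is the finding made, relative to treatment?** There is one dose, completed in 15 minutes at Visit 2. Table 1 marks safety bloods only at Visit 3, and the final assessment is four weeks after dosing, with a window of ±10 days. The result does not depend on that reading of Table 1: any blood drawn after the infusion ends comes after all treatment has been given.

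**Step 3. Apply each route to a grade.**

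| Route | What it needs | Visit 3 case |
|---|---|---|
| Mild | Not noticed or not uncomfortable, and no effect on functioning | Met |
| Moderate, by feeling | Discomfort | Not met |
| Moderate, by drug action | Possible dose reduction | Not available; no further dose |
| Severe, by feeling | Severe discomfort | Not met |
| Severe, by drug action | Possible stopping of study drug | Not available; infusion completed |
| Life-threatening | Immediate risk of death | Met only at that extreme |

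The remarks on treatment within the Mild, Moderate and Severe definitions concern relief of symptoms. They give no route to a higher grade for a value that needs correction but causes no symptoms.

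**Step 4. Does the value matter anywhere?** Only through Life-threatening, or through an effect on functioning that takes the event outside Mild. Between those limits the grade stays at Mild as the value worsens.

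**Step 5. Where is severity used next?** IRB Reporting compares an event's severity with the protocol, the consent form, the labeling and similar sources. It does not say that severity there means the item 1 grade, so the link is possible but not fixed. The analysis sections define a safety set but no table of events by severity.

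**The case against.** The strongest reply is that the scale is not purely about feeling. Moderate and Severe can be reached through action on study drug, Life-threatening covers signs without symptoms, and Mild also requires that functioning be unaffected. All of this stands. A reader might infer that every adverse event is graded by how the patient feels, or that a symptom-free harm of any size is Mild. The documents support neither.

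Blood pressure shows the limit. A symptom-free rise during the infusion that might cause it to be stopped fits Severe. A physician safety monitor is available for the infusion, so such a change could be acted on. The point is therefore made for laboratory findings on the later bloods, not for hypertension in general.

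The drug-action wording could also be read hypothetically: an abnormality of a kind that might lead to stopping a drug, were there one to stop. The plan does not say this, and on that reading the grade would still have no measured value behind it.

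On consequences, a reader might infer that the safety conclusion would be too favourable to the drug. The documents do not support this: no severity-graded safety analysis is specified, event counts do not depend on the grade, and the phosphate value remains on record. A reader might also infer that reports due within five working days would be missed. That does not follow either. Besides the loose link noted above, an important medical event can be made serious on medical judgement, and Other Reportable events separately requires a report of new information such as a more severe or more frequent side effect. These are real safeguards for reporting, but they do not change the severity grade.

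**Conclusion.** The point holds in a limited form. The severity scale has no objective criteria for laboratory or vital-sign findings. In this single-dose design, a symptom-free laboratory abnormality found after the infusion, without effect on functioning and short of immediate risk of death, is Mild regardless of magnitude. The recorded severity of laboratory harms would therefore not reflect their size. It could weaken the severity judgement for IRB reporting, but would not alone determine it.

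The number of affected events cannot be estimated. The protocol says only that the named reactions occur in more than 2%. It does not say how many phosphate falls would be marked, symptom-free and still present at Visit 3, and a small symptom-free fall graded Mild is not an error.

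The conclusion assumes that the definitions are applied as written and that no grading scale is set out in a document outside those supplied. It concerns safety recording only and does not touch the efficacy endpoints. The change is worth making because the gap is clear and closing it is cheap.

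**What to change.** In Classification of Adverse Events, item 1, add text to this effect:

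*Laboratory and vital-sign adverse events are graded from the measured value on one published numeric toxicity scale, named here. Where the definitions below would give a higher grade, the higher grade is recorded. The definitions below apply alone to all other events.*

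The sponsor should choose the scale and name it in the protocol. The resulting grade should be used wherever severity is reported, and IRB Reporting should state that its severity judgement takes this grade into account.

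Taking the higher of the two grades matters. A rule based on the value alone could lower the grade of an event with a modest value but severe discomfort.

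The cost is a short protocol amendment and a lookup on values already measured. No procedure, visit or treatment rule changes. The downside is that some laboratory events will carry a higher grade than under the present wording.
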